4.1.3 Definition of Maximum Tolerated Dose (MTD)

The **maximum tolerated dose** (MTD) is defined as the highest dose at which 0 out of first 3 or 1 out of total of 6 patients experience DLT during the first cycle of therapy; this dose level will be recommended as RP2D in the second portion of the study. If accrual to cohort 2 (highest dose of both everolimus and TRC105) is completed without reaching the MTD, this dose will be selected as the RP2D. In every cohort, patients withdrawn without receiving study treatment will be replaced, as will patients withdrawn before completing the first cycle of treatment for any reason other than DLT.

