4.1.1 Definition of a Dose Limiting Toxicity (DLT)

A **dose-limiting toxicity (DLT)** is defined as:

- a) Any grade 3 or 4 non-hematologic toxicity except anorexia, alopecia, nausea (which is not refractory to antiemetics), fatigue, fever without neutropenia;
 - b) Failure to recover to baseline (except alopecia) after delaying the next dose by more than 14 days;
 - c) Grade 3 or 4 neutropenia complicated by fever >38.5°C or infection, or grade 4 neutropenia of ≥7 days duration; or
 - d) Grade 4 thrombocytopenia, or grade 3 thrombocytopenia complicated by hemorrhage.
- In addition, accrual will be halted as a result of any grade ≥3 hemorrhage, cerebrovascular and vasovagal adverse events; FDA will be contacted to discuss further accrual or potential need for protocol amendment.

4.1.2 Dose escalation rule:

Dose escalation will follow the decision rules shown in **table 4-2**.

Table 4-2. Dose escalation rules

Number of Patients with DLT at a Given Dose Level	Escalation Decision Rule
0 out of 3	Enter 3 patients at the next dose level.
1 out of 3	Enter 3 additional patients in the same dose level (for a total of 6 patients at this dose level). If 0 of the 3 additional patients experience DLT, then proceed to the next dose level. If 1 or more of these additional patients experience DLT (i.e., ≥ 2 of 6 total patients), dose escalation will be

	stopped.
≥ 2 out 3	Dose escalation will be stopped.
If MTD not reached	Cohort 2 will be selected for RP2D

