4.2 Phase II, expansion phase

The second part of the study (phase II, **expansion phase**), will ensue once the MTD and RP2D have been determined. The objectives of the dose expansion phase is to estimate the rate of complete pathologic remission (pCR) or downstaging in addition to continue evaluation of the safety. In order to minimize exposure of patients to ineffective therapy, Gehan’s two-stage design will be used⁵¹. The study will enroll 10 patients first, and if no patient has pCR or downstaging, the study will close on the basis that it is unlikely (p=0.1074) that 0/10 responses would occur if the true response rate were >20%. If at least one patient has pCR or downstaging, an additional 10 patients will be treated (total of 20). For patients enrolled in Phase II, dose of everolimus can be de-escalated down to 2.5mg if needed. No further de-escalation is allowed. If 2.5mg not tolerated then the patient will be removed from study.

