5.3 Dose Modifications and Delays

Dose modifications and delays are allowed. Determinations to reduce the dose, withhold, or delay the administration of a drug rely on the treating physician. The choice of the drug(s) (letrozole and/or everolimus and/or TRC105, or all three components) that need(s) to be withheld or dose reduced (everolimus or TRC105; delays but no dose reductions are allowed for letrozole) relies on the treating

physician and should be based on the nature of the observed adverse events. **The justification for dose modifications and delays should be clearly documented.** The maximum duration that a patient is allowed to withhold up to all three medications of the regimen is 7 days. Treatment can be resumed after 7 days at a lower dose level as outlined below for each individual component of the regimen. If treatment cannot be resumed within 7 days, the patient will be taken off study.

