5.5 Study Termination

The principal investigator retains the right to terminate study participation in consultation with the other investigators in the study. The principal investigator will notify the institutional review board and FDA in writing of the early termination or completion of the study and keep a copy of the notification in the regulatory file. Circumstances that may raise consideration for early termination include but are not limited to: inordinate toxicity of the proposed combination that is not amenable to protocol amendment, and slow accrual (rate of accrual of less than 1 patient in 6 months).

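### The RP2D can rest on no DLTs in three patients, and the 10- to 20-patient expansion has no aggregate DLT boundary that would prompt a review of that choice

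*Combined protocol and SAP*

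**What the plan says.** **Dose selection.** Section 4.1.3 takes as MTD the "highest dose at which 0 out of first 3 or 1 out of total of 6 patients experience DLT" in cycle 1, and "this dose level will be recommended as RP2D in the second portion of the study". In Table 4-2 (section 4.1.2), the action after 0 of 3 is "Enter 3 patients at the next dose level". After 1 of 3, three more patients enter: "If 0 of the 3 additional patients experience DLT, then proceed to the next dose level". If the MTD is not reached, "Cohort 2 will be selected for RP2D". No section requires six patients at the level that becomes the RP2D.

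**Expansion.** Section 4.2 gives phase II the task of estimating pCR or downstaging "in addition to continue evaluation of the safety". Ten patients are treated, then ten more if at least one responds. That efficacy rule is the only counted stopping rule in phase II. Section 10.2 estimates adverse event rates at the end of the study.

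**Other safeguards.** Any grade 3 or higher hemorrhage, cerebrovascular or vasovagal event halts accrual and brings in the FDA (synopsis, sections 4 and 4.3). Section 5.5 lets the principal investigator consider ending the study for "inordinate toxicity of the proposed combination that is not amenable to protocol amendment". Section 9.3.3 places the trial under a Clinical Trials Monitoring Committee.

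**The concern.** MTD and RP2D are part of the primary endpoint (section 1.2.1), and section 4.4 says that TRC105 has not been given with letrozole and everolimus before. Three patients observed for one 4-week cycle say little about a DLT rate. That is usual in a 3+3 design and acceptable when the next stage can correct a poor choice. Here the next stage has a safety objective but no DLT count attached to it. An excess of, say, stomatitis, pneumonitis or hyperglycemia meeting the DLT definition would be managed patient by patient. No number is stated at which anyone must ask whether the dose itself is wrong.

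**Working it through.** **The plan's own figures.** The plan states no operating characteristics for its DLT rule. The nearest stated figures reproduce:
- Gehan stage 1 at a 20% response rate: 0.8^10 = 0.1074, as in sections 4.2 and 10.1.
- Enrolment in section 4.3: 6 + 20 = 26 and 18 + 20 = 38.

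**Precision of 0 of 3.** Exact two-sided 95% upper limit: 1 − 0.025^(1/3) = 0.708.

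**Acceptance of one level, given that it is reached.** Inputs are the rules in Table 4-2 and section 4.1.3. The true DLT rate q is assumed. A level passes with 0 of 3, or with 1 of 3 followed by 0 of 3:

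A(q) = (1−q)^3 + 3q(1−q)^2 × (1−q)^3

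| q | 0/3 route | 1/6 route | Total |
|---|---|---|---|
| 20% | 0.512 | 0.197 | 0.709 |
| 30% | 0.343 | 0.151 | 0.494 |
| 40% | 0.216 | 0.093 | 0.309 |
| 50% | 0.125 | 0.047 | 0.172 |

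At 40%, for example, 0.6^3 = 0.216 and 3 × 0.4 × 0.36 × 0.216 = 0.093. About 70% of those acceptances (0.216 / 0.309) rest on three patients.

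**Allowing for cohort 1.** Cohort 2 is reached only if cohort 1 passes. With 40% in cohort 2, the unconditional chance that it becomes the RP2D is A(q1) × 0.309: 0.280, 0.219, 0.153 or 0.096 for a cohort 1 rate of 10%, 20%, 30% or 40%.

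**Exposure.** At an unchanged 40% rate, expected DLTs are 0.4 × 10 = 4 in stage 1 and 0.4 × 20 = 8 if both stages run. The efficacy rule seldom limits exposure. At the 25% downstaging rate that section 2.1.5 quotes for letrozole alone, the chance of continuing is 1 − 0.75^10 = 0.94.

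**An example boundary.** Pool phase I patients at the RP2D with phase II patients. Hold at ≥2 of 6, ≥4 of 10, ≥6 of 15 or ≥8 of 20. Exact binomial recursion, starting from 0 of 3 or 1 of 6 and adding all 20 phase II patients (to 23 or 26), gives these hold probabilities:

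| True rate | From 0/3 | From 1/6 | Over all accepted doses |
|---|---|---|---|
| 15% | 7% | – | – |
| 20% | 12% | – | – |
| 40% | 57% | 41% | 52% |
| 50% | 81% | 68% | 78% |

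The last column weights the two routes by their acceptance probabilities. At 40%: (0.216 × 0.568 + 0.093 × 0.409) / 0.309 = 0.52.

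**The 18-patient maximum.** Sections 4.1 and 10.1 allow 18 patients, six in each of three cohorts. Under Table 4-2, cohort 2 opens only if cohort 1 passes, and the synopsis opens cohort -1 only if cohort 1 is not tolerated. Without re-expansion the most is 6 + 6 = 12. Eighteen needs cohort 1 to start with three, cohort 2 to fail with six, cohort 1 to be refilled to six and then fail, and cohort -1 to take six. That refilling is not written anywhere.

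**The case against.** The protocol openly adopts a conventional 3+3 with a descriptive, hypothesis-generating expansion, and many such trials accept a dose on 0 of 3. Phase II is also not unguarded. One named grade 3 or higher event halts accrual, and vasovagal reactions, which section 5.2.3.1 lists among infusion reactions, are included. Section 5.3 states that "Dose modifications and delays are allowed", section 4.2 permits everolimus reductions in phase II, and Tables 5-2 to 5-10 give per-patient rules. Serious events are reported within 24 hours (section 8.1.2).

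All of this stands. It rules out the stronger inference that the expansion runs without any tolerability stop. What remains is narrower: patient-level rules do not test the dose, the named halt leaves out most DLT types, and neither section 5.5 nor section 9.3.3 states a threshold.

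Three other readings go too far:
- **That 31% is the risk from the three-patient rule, or the chance that cohort 2 is wrongly chosen.** It pools two routes and is conditional on reaching the level.
- **That the 26 in section 4.3 shows cohort 2 being chosen on three patients.** It also fits a failed cohort 1 followed by three patients in cohort -1, and the documents do not say which is meant.
- **That the DLT definition should also absorb cycle 1 dose reductions.** Section 5.3.2 is headed for phase II, and section 5.3 takes patients off study if treatment cannot resume within 7 days, so that section 4.1.3 then replaces them unless they had a DLT. Counting dose shortfall as a DLT would rewrite a clinical definition, which this point does not ask for.

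**Conclusion.** The point holds as a gap in the design, not as an error of calculation. The RP2D may be declared on 0 of 3. A level with an assumed 40% DLT rate, once reached, passes with probability 0.31, of which 0.22 is on three patients alone. The 10- to 20-patient expansion then has no aggregate DLT boundary beyond the event-specific halt, the discretionary clause and committee oversight.

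The rates of 30%, 40% and 50% are scenarios. The nearest figure in the documents is 22.6% grade 3 or 4 events with everolimus plus letrozole (section 5.2.2), which is not a cycle 1 DLT rate. The calculations assume independent patients and a rate that does not change between phases. The hold probabilities also assume that the efficacy rule lets all 20 patients enter.

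Whether cohort 1 would be re-expanded after cohort 2 fails is unclear. The 18-patient maximum implies it, though 18 may be simple 3 × 6 arithmetic, so one cannot say that no backfill was intended.

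**What to change.** 1. **Sections 4.2 and 10.1.** Pool the cycle 1 DLTs of phase II patients, under the section 4.1.1 definition as it stands, with those of phase I patients at the RP2D. Hold enrolment for review at a prespecified boundary, for example ≥2 of 6, ≥4 of 10, ≥6 of 15 or ≥8 of 20. State its operating characteristics from both starting points. The team may prefer other limits; they should follow from a stated unacceptable DLT rate.
2. **First phase II patients.** Until six patients are evaluable at the RP2D, have the first phase II patients complete cycle 1 before further enrolment.
3. **Sections 4.1, 4.1.2 and 10.1.** Reconcile the 18-patient maximum with Table 4-2 by stating whether cohort 1 is re-expanded after cohort 2 fails.

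**Cost.** No added patients. There is a short initial wait, modest at the 1 to 2 patients per month in section 4.3. From 0 of 3, the chance of a hold that proves unnecessary is 7% at a 15% rate and 12% at 20%.

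**Limits.** The example misses about half of accepted doses with a 40% rate. It counts cycle 1 only, 4 of 24 weeks, so later toxicity still depends on the existing safeguards. A hold prompts review; it is not a closure and sets no dose or treatment rule.

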4.3 Study accrual and treatment considerations

It is anticipated that 26 – 38 patients will be enrolled in the study and accrual is expected to be completed in 24 months (see Section **10. STATISTICAL CONSIDERATIONS**). Patients meeting the eligibility criteria and who have signed the consent form will start Letrozole 2.5 mg PO daily, Everolimus 5 or 10 mg PO daily, and TRC105 15 or 10 mg/kg IV every two weeks with the first infusion administered in 2 split doses on days 1 (3 mg/kg) and 4 (12 mg/kg or 7 mg/kg), respectively. Premenopausal women at the time of study enrollment will receive goserelin 3.6 mg subcutaneously q 4 weeks to achieve ovarian suppression. A cycle is defined as 4 weeks of treatment. Breast ultrasound, will be conducted upon completion of each cycle to complement clinical assessments of the size of the tumor(s). The duration of neoadjuvant therapy is 24 weeks or 6 cycles. No extensions of the neoadjuvant therapy beyond 6 months are allowed. After neoadjuvant therapy, patients will undergo surgical treatment and will receive adjuvant therapy (radiation therapy, chemotherapy, hormonal therapy) according to the standard of care or at the discretion of the treating physician. The accrual rate is projected to be approximately 1-2 patients per month. Accrual will be halted as a result of any grade ≥ 3 hemorrhage, cerebrovascular and vasovagal adverse events; FDA will be contacted to discuss further accrual or potential need for protocol amendment.

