5.2.3.3 Management of Anemia

Hypoproliferative anemia was the dose-limiting toxicity in the phase I study³⁵ and may be related to the action of TRC105 on proerythroblasts, the only cells in the bone marrow known to express high levels of CD105. When hemoglobin drops in a patient on the study, it is important to investigate for any ongoing blood loss. A reticulocyte count should be obtained to document the hypoproliferative nature of the anemia associated with TRC105. Anemia should be managed with standard supportive measures including transfusions of packed red blood cells if deemed necessary. If grade 3 or higher treatment related anemia develops, the dose of TRC105 should be reduced from 15 mg/kg to 10 mg/kg or held if the assigned dose is 10 mg/kg until resolution of the anemia.

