5.3.1 Dose modifications and delays with letrozole

Modifications. The dose of letrozole will not be modified (increased or decreased) in this protocol. Also letrozole cannot be substituted for another hormonal agent (e.g. anastrozole). Delays. The maximum duration that a patient is allowed to withhold letrozole due to adverse events is 7 days. If a patient cannot resume letrozole after 7 days or it is deemed necessary to withhold the medication again, the patient will be taken off study.

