5.3.3 Dose modifications and delays with TRC105

Modifications. The dose for TRC105 is 10 or 15 mg/kg IV every two weeks and it will be continued until 4 weeks prior to surgery. Dose reductions to 10 mg/kg due to adverse events are allowed and the justification(s) should be documented. Dose reductions below 10 mg/kg are not allowed and if deemed necessary, the patient will be taken off study.

Delays. All infusions of TRC105 should be administered within 3 days of the protocol-specified schedule. The maximum duration that a patient is allowed to withhold TRC105 due to adverse events is 14 days. If TRC105 is delayed > 3 days the first dose of TRC105 following the break needs to be split into two doses; 3 mg/kg should be given on the first day and the remainder of the dose (i.e., 12 mg/kg, or 7 mg/kg in the case of a dose de-escalation) will be given 3 days later and the

methylprednisolone dose should be reinstated. If a patient cannot resume TRC105 after 14 days or it is deemed necessary to withhold the medication again, the patient will be taken off study. Resumption at 10 mg/kg if the subject was receiving 15 mg/kg are allowed with the reinstatement of full premedication, as specified in Section 5.2.3.1.

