5.6 Subject Discontinuation

Patients may withdraw from this study at any time. Any patient who withdraws will be encouraged to return to the study center for the post-dose evaluations. The termination visit consists of all evaluations scheduled for the termination visit. The primary reason(s) for discontinuation must be recorded on the appropriate CRF page.

The PI may discontinue a patient from treatment. Reasons may include, but are not limited to, the following: progressive disease, failure to obtain postmenopausal status (defined as serum estradiol levels any time during treatment in the premenopausal range) clinically significant deterioration, noncompliance, persistent grade 3 or 4 adverse event or any significant adverse event that compromises the patient's ability to participate in the study, requirement of a significant surgical procedure or radiation therapy during the treatment period of the study, investigator's determination that it is not in the patient's best interest to continue participation, anemia greater than grade 4, persistent grade 3 mucositis despite maximal supportive care, development of brain metastases, pregnancy.

Patients who have an ongoing grade 4 or serious adverse event at the time of discontinuation from study treatment will continue to be followed at least weekly for 4 weeks and at least monthly thereafter at the discretion of the investigator until resolution of the event or until the event is considered irreversible.

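### Section 4.1.3 replaces cycle-1 withdrawals for everolimus or TRC105 toxicity that is not a listed DLT, so these patients drop out of the 3+3 count that sets the MTD

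*Combined protocol and SAP*

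**What the plan says.** The MTD is the highest dose with DLT in 0 of the first 3 or 1 of 6 patients during cycle 1 (section 4.1.3), and Table 4-2 escalates or stops on DLTs alone. Section 4.1.3 replaces patients withdrawn untreated, "as will patients withdrawn before completing the first cycle of treatment for any reason other than DLT". Section 4.3 fixes the window: "A cycle is defined as 4 weeks of treatment".

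Section 4.1.1 lists four DLT criteria: (a) grade 3-4 non-hematologic toxicity, with exceptions that include fatigue; (b) "Failure to recover to baseline (except alopecia) after delaying the next dose by more than 14 days"; (c) complicated grade 3-4 neutropenia, or grade 4 lasting at least 7 days; (d) grade 4 thrombocytopenia, or grade 3 with hemorrhage. Anemia is not named.

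Several rules can end treatment in cycle 1:
- Section 5.3 limits a hold of up to all three drugs to 7 days and then takes the patient off study.
- Section 5.3.3: "The maximum duration that a patient is allowed to withhold TRC105 due to adverse events is 14 days". A patient who "cannot resume TRC105 after 14 days or it is deemed necessary to withhold the medication again, the patient will be taken off study".
- Section 5.3.1 does the same for letrozole: a patient who "cannot resume letrozole after 7 days or it is deemed necessary to withhold the medication again, the patient will be taken off study".
- Section 5.6 lets the investigator discontinue for a "persistent grade 3 or 4 adverse event or any significant adverse event that compromises" her ability to take part.

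For everolimus, section 5.3.2 (headed as phase II) sets 7 days and no second hold. Tables 5-2, 5-3, 5-7 and 5-9 allow interruption up to 28 days, and Table 5-4 directs a second hold when grade 2 stomatitis recurs.

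**The concern.** MTD and RP2D form part of the primary endpoint (section 1.2.1). In a 3+3 design, replacement is meant for patients who tell us nothing about tolerability, such as those who move away or withdraw consent. A patient who stops because she cannot tolerate the combination is informative. Replacing her discards evidence in one direction only, against the dose. With three to six patients per level, one such patient can reverse an escalation decision.

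Criterion (b) looks like the safety net for toxicity outside (a), (c) and (d), but it needs a longer delay than the off-study rules generally allow.

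**Working it through.** The plan gives no operating characteristics for the 3+3 stage. Its one related figure is the enrollment ceiling in section 10.1, and 3 cohorts × 6 patients = 18 reproduces it. The check therefore has two parts.

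**1. Can criterion (b) catch these patients?** A dose due on day s is more than 14 days late on day s + 15. Assume a 28-calendar-day cycle; section 4.3 does not say whether a delay extends it.
- TRC105 due C1D15: 15 + 15 = day 30, after the window closes.
- TRC105 due C1D4: 4 + 15 = day 19, inside the window. This route is closed if the 7-day rule in 5.3 governs and open if the 14-day rule in 5.3.3 governs.
- Everolimus: s + 15 ≤ 28 requires a hold starting by day 13. That works only if the 28-day limits in Tables 5-7 and 5-9, which carry no phase restriction, override the 7 days in 5.3.
- A second TRC105 hold (for example C1D4, then C1D15) takes the patient off study whatever its length.
- Discontinuation under 5.6 requires no delay at all.

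**2. How much does replacement change escalation?** Let d be the chance of a listed DLT in cycle 1 and w the chance of withdrawal for related toxicity that is not a listed DLT. Neither is in the documents.

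P(escalate) = q³ + 3p·q²·q³, with q = 1 − p.
- Replaced, as written: p = d/(1 − w).
- Counted as DLT: p = d + w.

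Rough anchor for w: section 5.2.2 reports discontinuation of 18.8% with everolimus plus letrozole and 9.1% with letrozole alone; section 4.4 puts that treatment at 4 months. Spread evenly over four 4-week periods, 1 − (1 − 0.188)^(1/4) = 5.1%. For the excess of 9.7%, 1 − (1 − 0.097)^(1/4) = 2.5%. Some of these would be listed DLTs or not toxicity at all, while TRC105 is added here. I therefore take w = 1% and 2.5%, with 5% as an upper bound, and assume d = 15% or 20%.

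Example, d = 0.15 and w = 0.025:
- Replaced: p = 0.15/0.975 = 0.1538, so 0.606 + 0.200 = 0.806.
- Counted: p = 0.175, so 0.562 + 0.201 = 0.762.

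| w | d | replaced | counted | difference (points) |
|---|---|---|---|---|
| 1% | 15% | 0.811 | 0.793 | 1.7 |
| 1% | 20% | 0.704 | 0.687 | 1.7 |
| 2.5% | 15% | 0.806 | 0.762 | 4.4 |
| 2.5% | 20% | 0.698 | 0.654 | 4.3 |
| 5% | 15% | 0.798 | 0.709 | 8.9 |
| 5% | 20% | 0.686 | 0.600 | 8.6 |

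Carried through both levels, with DLT rates of 15% then 25%, the chance that cohort 2 becomes the RP2D is 0.482 against 0.459 at w = 1%, 0.472 against 0.416 at 2.5%, and 0.456 against 0.350 at 5%.

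Expected withdrawals of this kind in 18 patients are 18w = 0.18, 0.45 and 0.90. The chance of at least one in a cohort of 6, 1 − (1 − w)^6, is 5.9%, 14.1% and 26.5%.

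**The case against.** The strongest reply is that the MTD is defined by the listed DLTs, so the claimed bias appears only if the list is changed. Measured against that list, replacement makes escalation slightly less likely: with d = 15%, P(escalate) is 0.814 when w = 0 and 0.798 when w = 5% and patients are replaced. This is correct. The point is therefore that the rule ignores treatment-ending toxicity, and not that the rule miscalculates its own MTD.

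The routes are also narrower than they first appear:
- The 5.6 route applies only where the event compromises participation, and it is discretionary.
- For anemia, reduction comes first: "If grade 3 or higher treatment related anemia develops, the dose of TRC105 should be reduced from 15 mg/kg to 10 mg/kg or held". The dose-limiting anemia in the first-in-human study arose at 15 mg/kg weekly, twice this trial's frequency, in patients on study through cycle 2 (sections 2.1.7 and 8.3.1).
- Grade 2 stomatitis leads first to a hold and restart under Table 5-4.
- Letrozole is 2.5 mg in every cohort, so a withdrawal due to letrozole alone says little about the escalated dose and should not count.

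These limits reduce the likely frequency but do not close the gap.

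On the hold limits, section 5.3 points ahead to component-specific rules, so 5.3.3 can naturally be read as overriding the general 7 days for TRC105. That reading does not settle everolimus, because 5.3.2 and the tables are both specific to it. It is a separate drafting matter, mainly for phase II: 5.3.2 is headed that way, and Tables 5-2 to 5-4 refer to section 4.2.

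A reader might infer that criterion (b) can never be met. The C1D4 case, and an early everolimus hold under the 28-day limits, show otherwise.

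**Conclusion.** The concern stands in limited form. As written, 4.1.3 removes from the 3+3 count patients whose treatment ends in cycle 1 because of everolimus or TRC105 toxicity outside criteria (a), (c) and (d), and criterion (b) often cannot bring them back. No other clause does so; the accrual halt covers only grade 3 or higher hemorrhage, cerebrovascular and vasovagal events.

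At assumed rates of 1% to 2.5% per cycle the effect is about 2 to 4 points on P(escalate). The 9 points at 5% is an upper bound, because that rate rests on discontinuations that include the letrozole background. Much larger effects follow from withdrawal rates of 10% or more, but nothing in the documents supports such rates.

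A reader might also infer that the reported adverse event rates are biased. They are not: section 10.2 analyses everyone who received at least one dose, so the harm is confined to the dose decision.

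**What to change.** - **Section 4.1.3:** replace only patients withdrawn in cycle 1 for reasons unrelated to everolimus or TRC105 toxicity.
- **Section 4.1.1 and Table 4-2:** count as a DLT any cycle-1 withdrawal for toxicity at least possibly related to everolimus or TRC105, but not to letrozole alone. Section 8 already asks for a causality judgment on these two drugs.
- **Criterion (b):** state that failure to recover within the permitted hold is a DLT, and whether a dose delay extends cycle 1.
- **Hold limits:** state that the 14 days for TRC105 in 5.3.3 overrides the 7 days in 5.3. Set one everolimus limit, with its phase and whether a second hold is allowed, and use it in 5.3, 5.3.2 and Tables 5-2, 5-3, 5-4, 5-7 and 5-9. The clinical team should choose the limits.

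The cost is a protocol amendment that widens what counts as a DLT and gives weight to some discretionary withdrawals. Escalation would stop somewhat earlier: P(escalate) falls by about 2 to 4 points at the 1% to 2.5% rates, and by about 9 at the upper bound. No extra data are needed.
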